## **H. MEASUREMENT**

The assessment instruments that will be used for specific aim 1:

1. EORTC QLQ-C30, Quality of life in cancer patients

The complications assessment instruments that will be used for specific aim 2:

1. HUM00012731 data collected around the time of operation and post-operative visit.
2. Long-term data from HUM00012731

Patients will also be invited to enroll in the “Patient outcomes following esophagectomy for benign and malignant disease” HUM00012731, a study in which the PI ([name]) is also a co-investigator. To minimize patient burden, the baseline preoperative assessment and the evaluation for quality of life will be performed according to the protocol outlined in HUM00012731. Demographics and history forms HUM00012731 will only be administered once preoperatively. This data will then be shared to support the study aims of this protocol to minimize patient inconvenience. In the event, that a patient does not wish to be co-enrolled in HUM00012731, the attached forms (EORTC QLQ-C30 and Demographics and history forms HUM00012731) will be administered by the Thoracic Surgery Clinical Coordinator, who will be trained and added to the HUM000XXXXX study protocol, at the scheduled time points outlined in Section N.

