## **I. DATA COLLECTION**

All data collection following surgery will be performed by research staff other than the study surgeon. This will reduce bias by maintaining masking in data collection of outcome measures. All research staff will be trained and certified to perform data collection procedures. Allowable windows for timed evaluations are specified in Section N and include a one-week window on each side of the postoperative visit planned at 2-3 weeks. The assessments at 1-month, 3-months, and 6-months will take place by mail and will not require a visit to the clinical site.

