### **I.1 Demographics, Medical History, and Physical Examination**

#### **a. History**

- i. Age
- ii. Sex

- iii. Previous medical history
- iv. Prior thoracic procedures
- v. Primary diagnosis
- vi. Previous thoracic chemotherapy or radiation
- vii. Planned procedure
- viii. Comorbidities will be collected using the Charlson Comorbidity index collected at baseline

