**J. STATISTICAL AND DATA MANAGEMENT CONSIDERATIONS**

**For the specific aims:**

Specific Aim 1: Quality of Life measurements will be compared at 6 months, using descriptive statistics.

Specific Aim 2: Calories will be compared between groups.

**For the secondary aims:** Height and weight will be compared between groups at 30 days and 6 months.

**Sample size justification:** This was measured with the possible recruitment pool and differences between groups.

**Interim analysis:** At 50% recruitment or three years.

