**Randomization:**

This study will randomize eligible patients to receive post-operative tube feeding for 1 month or standard post-operative care in a one-to-one fashion. Patients will be randomized using a blocked randomization technique in order to ensure equal sample sizes across groups. [name] – is this correct? The study statistician ([name]) will generate the randomization assignment table for the study's data manager. The investigators will call the data manager for the treatment assignment when a patient has been fully consented and is determined to be eligible for study enrollment.

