## K. RECRUITMENT

An estimated sample size of XXXXX – insert from [name] evaluable\* patients will be enrolled over a period of 12-24 months.

\* Patients that meet inclusion criteria (see section E.1) and are not excluded from participation in the study by the exclusion criteria (see section E.2). If there are patients who drop out of the study or are loss to follow-up, they will be replaced to achieve a minimum sample size of XXXXX – insert from [name] evaluable patients for specific aims 1 and 2.

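### Section J compares weight between arms at 30 days and 6 months without using pre-operative weight; the comparison is unbiased but loses precision that baseline adjustment would recover (minor, secondary).

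*Combined protocol and SAP*

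**What the plan says.** The only analysis text on weight is one sentence under the secondary aims in Section J: "Height and weight will be compared between groups at 30 days and 6 months". It gives no scale (level, change or percent change), covariate, test or model.

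Section I.1.b lists height, weight and BMI under physical examination, beside the history items in I.1.a. No time point is attached to weight. Two nearby statements point to a pre-operative measurement. Section H says "Demographics and history forms HUM00012731 will only be administered once preoperatively", and I.1.a says "Comorbidities will be collected using the Charlson Comorbidity index collected at baseline". Section H.3 also has data collection starting at the initial screening visit. Table 1 in Section N has no row for weight or physical examination at any visit.

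On later contacts, Section I says "The assessments at 1-month, 3-months, and 6-months will take place by mail and will not require a visit to the clinical site".

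No design figures for weight are given. The sample size justification reads "This was measured with the possible recruitment pool and differences between groups", and Section K leaves the number as a placeholder: "An estimated sample size of XXXXX". Allocation is to tube feeding "or standard post-operative care in a one-to-one fashion".

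**The concern.** Adults differ a good deal in body weight, and a person's weight after surgery is likely to track their weight before it. A comparison of follow-up weights that ignores the starting weight carries all of that between-person variation in its standard error. If the true difference between arms is a few kilograms, the interval may be too wide to show it, even though a measurement that explains much of the variation appears to be on file.

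At stake is an avoidably uninformative result on weight. Section B already describes earlier randomised studies as very small and showing no benefit. An unnecessarily wide interval here would add another result that settles nothing. A chance difference in starting weight would also pass straight into the estimate of that one trial, and adjustment removes most of it.

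**Working it through.** There is no stated power, SD, effect or sample size for weight, so there is no figure of the plan's to reproduce. Everything numerical below rests on assumptions.

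**Inputs**
- Allocation 1:1 (Section J, randomisation).
- Assumed: SD of weight 16 kg (14 and 18 kg as a check), true difference d = 3 kg, two-sided 5% test, ρ from 0.5 to 0.95.
- Assumed sample sizes: 70 and 35 per arm, with 12 as a lower end. Section B gives 12 to 70 per group as the size of earlier trials; these are not this trial's numbers.

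**Formulas**
- Unadjusted: SE = SD × √(2/n).
- ANCOVA on baseline: SD is replaced by SD × √(1 − ρ²).
- Change score: SD is replaced by SD × √(2(1 − ρ)).
- Power = Φ(d/SE − 1.96) + Φ(−d/SE − 1.96).

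**Variance relative to the unadjusted comparison**

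| ρ | ANCOVA, 1 − ρ² | Change score, 2(1 − ρ) |
|---|---|---|
| 0.5 | 0.75 | 1.00 |
| 0.8 | 0.36 | 0.40 |
| 0.9 | 0.19 | 0.20 |
| 0.95 | 0.10 | 0.10 |

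A change score beats the unadjusted comparison only when ρ exceeds 0.5. In these formulas ANCOVA is never worse than either.

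**One line in full** (70 per arm)
- Unadjusted: SE = 16 × √(2/70) = 2.70 kg; d/SE = 1.11; power 20%; 95% CI half-width 1.96 × 2.70 = 5.3 kg.
- ANCOVA at ρ = 0.9: SD = 16 × √0.19 = 6.97 kg; SE = 1.18 kg; d/SE = 2.54; power 72%; half-width 2.3 kg.

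**Power for a 3 kg difference, SD 16 kg**

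| n per arm | Unadjusted | ρ 0.5 | ρ 0.8 | ρ 0.9 | ρ 0.95 |
|---|---|---|---|---|---|
| 70 | 20% | 25% | 46% | 72% | 94% |
| 35 | 12% | 15% | 26% | 44% | 71% |

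At 12 per arm, power is 7% unadjusted and 18% at ρ = 0.9.

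**Sensitivity to SD** (70 per arm, ρ = 0.9): SD 14 kg gives 24.5% unadjusted and 82.9% adjusted; SD 18 kg gives 16.7% and 61.9%.

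**Larger differences, unadjusted** (SD 16 kg, 70 per arm): power is 46% for 5 kg, 84% for 8 kg and 96% for 10 kg.

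**Is pre-operative weight a legitimate covariate?** Yes. Section F opens the randomisation envelope before discharge or at postoperative day 8, so a weight taken before surgery precedes allocation and cannot be affected by it.

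**The case against.** Several objections have force.

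- **The plan never says that raw weight is analysed.** That is so: Section J is silent on the scale. A plain comparison of levels is the natural reading, and pairing weight with height supports it. An analyst following the sentence would have no instruction to use baseline, so the change is needed under either reading.
- **A baseline weight is not a documented fact.** I.1.b has no time point and Table 1 has no weight row. Pre-operative collection is a fair inference from Section H and H.3, and no more than that. This stands, and it qualifies the claim about cost.
- **The size of the gain is all assumption.** This stands too. At ρ = 0.5 and 35 per arm the gain is under 3 points. At 35 per arm and ρ = 0.9, adjusted power is still only 44%. Adjustment does not rescue a trial that is too small.
- **Weight is not a listed outcome.** It is absent from the aims and from sections D and H, and no stated hypothesis depends on it. This limits the importance of the point.
- **Follow-up weights may not exist.** The 1-month and 6-month contacts are remote and no weight is scheduled. That is a separate gap, but the analysis change has no effect until it is closed. Noisier remote weights would lower ρ and shrink the gain.

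A reader might infer more than the documents support:
- That variation between patients would hide any feeding effect. It would not: under the same assumptions a 10 kg difference has 96% power without adjustment.
- That the unadjusted result is biased. Under randomisation it is unbiased and keeps its nominal error rate; only precision suffers.
- That weight is Section J's only evidence on nutrition. The same section also compares calories between groups, although that measures intake rather than nutritional status.

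**Conclusion.** The point holds as a minor, secondary one. Section J does not use pre-operative weight in the planned weight comparison, and using it would reduce the variance to 1 − ρ² of its unadjusted value whatever the SD. The direction does not depend on the assumptions, but the size does. With SD 16 kg, a 3 kg difference and a two-sided 5% test, the gain at 70 per arm ranges from 5 points (20% to 25%) to 74 points (20% to 94%) as ρ goes from 0.5 to 0.95. At 35 per arm it ranges from about 3 to 59 points (12% to between 15% and 71%). The documents do not show where in these ranges the trial would fall. The conclusion also rests on weight being recorded before surgery, which I.1.b implies without stating.

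**What to change.** Replace the sentence in Section J with text such as: *Weight at each follow-up time will be compared between the randomised groups by linear regression (ANCOVA) with pre-operative weight as covariate, and reported as the adjusted mean difference with 95% CI. Percent change from pre-operative weight will be summarised by group.* Drop the follow-up height comparison, since adult height will not respond to a month of feeding, and use height only to compute BMI.

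State in I.1.b that weight is taken pre-operatively. Also add weight to Table 1 at baseline and at the two follow-up times, with how it is obtained, so that there are values to analyse.

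The analysis change costs one sentence and one covariate, with no extra patients or visits, provided the pre-operative weight is in fact recorded. If it is not, the added cost is one measurement per patient at screening. Obtaining weights at the remote contacts is a separate cost, which the planned comparison already incurs however it is analysed.

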**Randomization:**

This study will randomize eligible patients to receive post-operative tube feeding for 1 month or standard post-operative care in a one-to-one fashion. Patients will be randomized using a blocked randomization technique in order to ensure equal sample sizes across groups. [name] – is this correct? The study statistician ([name]) will generate the randomization assignment table for the study's data manager. The investigators will call the data manager for the treatment assignment when a patient has been fully consented and is determined to be eligible for study enrollment.

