### **C. STUDY SCHEMA**

Patients will be evaluated for surgery by the study surgeons. Patients scheduled to undergo an elective esophagectomy and who meet inclusion criteria (See Section E.1) will be approached for enrollment. Written informed consent will be obtained from all enrolled patients (see Appendix B). Pre-operative Quality of Life Survey will be obtained using the EORTC QLQ-C30 (see attached). Patients will then be randomly assigned to either routine post-operative tube feeding for 1 month, or usual practice, tube feeding to continue in the hospital until the patient is taking adequate nutrition by mouth at POD#8, or upon discharge. Since this study cannot be blinded, patients that cannot take nutrition by mouth at POD#8, or are tube feeding dependent on discharge will not be included in analysis.

Figure 1. Illustrates the study design

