## **F. RANDOMIZATION AND MASKING**

Randomization envelopes will be created at the start of the study. Each envelope will be opened prior to discharge or at POD#8 if patients are able to take adequate nutrition by mouth, to determine if post-operative tube feeding will be continued or not.

By consenting to the study, patients agree to continue tube feeding for at least 50% of caloric needs for 1 month post-operatively. Cross-over after randomization will be permitted for patient condition, although once randomized, patients will be analyzed by the original group.

- A copy of the signed research consent form must be included in the patient's hospital chart.

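### Two allocation routes (envelopes and a call to the data manager) are not reconciled, and in an unmasked blocked trial assignments may be known or predictable before the in-hospital eligibility re-check

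*Combined protocol and SAP*

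**What the plan says.** Section F (Randomization and Masking) describes envelopes: "Randomization envelopes will be created at the start of the study". It times their use in hospital: "Each envelope will be opened prior to discharge or at POD#8 if patients are able to take adequate nutrition by mouth". It does not say who holds the envelopes, whether they are sealed, opaque or numbered, or which list they are made from.

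Section J (Randomization paragraph) describes a telephone route. The statistician generates an assignment table for the data manager, and "The investigators will call the data manager for the treatment assignment when a patient has been fully consented and is determined to be eligible"; the sentence ends by specifying eligibility for enrollment in the study. The same paragraph sets a 1:1 ratio and says "Patients will be randomized using a blocked randomization technique". No block size is given, and an unanswered drafting query follows the blocking sentence.

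Section C (Study Schema) says that patients scheduled for surgery "who meet inclusion criteria (See Section E.1) will be approached for enrollment". After consent and the pre-operative quality-of-life survey it continues: "Patients will then be randomly assigned to either routine post-operative tube feeding for 1 month, or usual practice". It adds that the study cannot be blinded. Patients who cannot eat at POD#8, or who depend on tube feeding at discharge, are to be left out of the analysis.

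Table 1 (Section N) marks randomization in the inpatient column only, with a footnote that continued eligibility is assessed first. Section L says that patients who fail at that stage are excluded from randomization.

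**The concern.** Entry to the comparison turns on whether a patient is eating adequately at POD#8 or before discharge, or is dependent on tube feeding. Neither state is defined, so the decision is a judgement. If the person making it knows the patient's arm, or can guess it, the decision can depend on the arm: a borderline patient may be kept when one assignment is due and set aside when the other is. The arms would then differ in ways that randomization was meant to prevent, and no analysis of the retained patients could undo that.

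Two features of the plan open this possibility. One is wording that permits the assignment to be requested at enrollment, ahead of the re-check. The other is blocked allocation in an unmasked trial whose investigators themselves obtain each assignment, which can make the next one predictable even when it is requested at the right time.

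If assignment did come first, leaving re-check failures out of the analysis, as Section C does, would be a post-randomization exclusion. That would conflict with Sections F and L, which analyze patients by original group once randomized.

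**Working it through.** **Step 1. Compare the sections on route and timing.**

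| Place | Route | Timing relative to the re-check |
|---|---|---|
| Section F | Envelope made at study start | After: opened at POD#8 or before discharge if oral intake is adequate |
| Section J | Call to the data manager, who has the statistician's table | No day named; the trigger is consent plus eligibility for enrollment |
| Section C | Not stated | Assignment follows consent and the pre-operative survey; no re-check is named between; failures are dropped from analysis |
| Section L | Not stated | After: failures are excluded from randomization |
| Table 1 and footnote | Not stated | After: inpatient column only, re-check first |

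The route conflict is between Sections F and J, and nothing links the envelopes to the table. On timing, three places put randomization after the re-check. Sections C and J can be read either way, because enrollment and consent are pre-operative in Section C and in the screening column of Table 1.

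**Step 2. Ask whether late timing alone would settle the matter.** It would not if the next assignment can be predicted from earlier ones. The plan states no block size, sample size or power, so there is no figure of its own to reproduce. Block sizes of 2, 4 and 6 are assumptions.

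Take a 1:1 permuted block of size 2m, with its size known and past assignments visible. An assignment is certain once the other arm's m places are used up. The expected number of arm-A places after the last arm-B place is m/(m+1), and the same holds with the arms exchanged. The expected number of certain assignments per block is therefore 2m/(m+1), and the share is

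(2m/(m+1)) / (2m) = 1/(m+1).

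- Block of 2 (m = 1): 1/2 = 50%
- Block of 4 (m = 2): 1/3 = 33%
- Block of 6 (m = 3): 1/4 = 25%

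Check for blocks of 4: the six sequences AABB, ABAB, ABBA, BAAB, BABA and BBAA have 2, 1, 1, 1, 1 and 2 certain assignments. That is 8 of 24, or 33%. Enumerating every block of sizes 2, 4 and 6 gives the same three shares.

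**Step 3. Add the less-than-certain guesses.** Suppose the observer always guesses the arm with more places left in the block, and guesses at random when they are equal. Enumeration gives 75.0%, 70.8% and 68.3% correct for blocks of 2, 4 and 6, against 50% with full concealment. For blocks of 4, the chances of being right at positions 1 to 4 are 1/2, 2/3, 2/3 and 1, which sum to 17/6; divided by 4 this is 70.8%.

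**The case against.** The strongest reply is that the plan means to randomize late. Section F, Section L and Table 1 with its footnote all put the re-check first. Section J names no day, and two of the eligibility criteria cannot be settled before surgery: E.1.2 requires a jejunal tube put in at operation, and E.2.5 turns on the patient's state at discharge. A patient determined to be eligible could therefore mean one who has reached that stage. Section C is a summary, and its exclusion from analysis is compatible with never having been randomized. This stands as evidence of intent. It does not remove the wording in Sections C and J that permits an earlier request.

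Two stronger conclusions might be drawn, and the documents do not support them. A reader might infer that every assignment is known from before surgery, about 8 days or more ahead of the exclusion decision. That depends wholly on the early reading, against three places that say otherwise. A reader might also infer that one patient could be given two different arms. Section J describes a single table, and nothing says that the envelopes come from another list.

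The percentages are also conditional. They need a fixed block size, known to or deduced by the person judging eligibility, and sight of past assignments. The plan does not say that blocks are fixed or their size disclosed. Section G (Standardization of Postoperative Care) masks attending providers as far as possible to the discharge regimen, which might limit what some of them see. It is partial, however, and sits beside a rule that investigators request each assignment. The figures would apply to any open-label trial with fixed blocks and do not measure bias in this one.

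Finally, the authors' own open queries in Sections J and L show that randomization is unsettled. That is a reason to settle it now, not a reason to leave the conflict.

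**Conclusion.** The point holds in a limited form. Sections F and J give two unreconciled allocation routes. The intended timing is probably after the re-check, but Sections C and J also permit assignment before it, so this is a conflict of wording and not an established pre-operative randomization. Separately, unmasked blocked allocation with no stated block size leaves upcoming assignments open to prediction when an undefined judgement decides who enters.

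The size can be given only as a range: 50%, 33% or 25% of assignments certain for blocks of 2, 4 or 6, assuming fixed blocks, a known or deduced size, and visible past assignments. Varied and undisclosed block sizes would lower these figures. Nothing in the documents shows that selection would in fact occur. The route and timing should be settled before the first patient is randomized.

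**What to change.** State one concealed route in Sections C, F and J, in line with Section L and Table 1:

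- Staff first record that the in-hospital re-check has been passed. Only then does the data manager release the next assignment from the statistician's list.
- Release may be by call, or by sequentially numbered, sealed, opaque envelopes drawn from that same list. Either is acceptable; the plan should name one.
- In Section J, replace the enrollment trigger with: *has passed the in-hospital eligibility re-check*.
- In Section C, state that patients who fail the re-check are not randomized.
- Generate the list with randomly varied block sizes known only to the statistician and the data manager, and resolve the open query beside the blocking sentence.

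This does not set a criterion for adequate oral intake or for dependence on tube feeding, which is for the investigators. It ensures that the judgement is on record before the arm is released.

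The cost is mostly wording, since the statistician's list, the data manager and the re-check are already in the plan. The downsides are a slight possible imbalance in arm sizes from varied blocks and reliance on the data manager being available when a patient becomes ready for assignment.

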## K. RECRUITMENT

An estimated sample size of XXXXX – insert from [name] evaluable\* patients will be enrolled over a period of 12-24 months.

\* Patients that meet inclusion criteria (see section E.1) and are not excluded from participation in the study by the exclusion criteria (see section E.2). If there are patients who drop out of the study or are loss to follow-up, they will be replaced to achieve a minimum sample size of XXXXX – insert from [name] evaluable patients for specific aims 1 and 2.

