### **E.2. Exclusion Criteria**

- E.2.1 Emergent procedure.
- E.2.2 Less than 18 years of age.
- E.2.3 Inability to provide informed consent or to complete testing or data collection.
- E.2.4 Unwillingness to be randomized.
- E.2.5 Tube feeding dependent on discharge.

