## L. DISCUSSION OF POTENTIAL LIMITATIONS IN STUDY DESIGN

A potential pitfall is that patients who consent to the study in the preoperatively, may not continue to meet eligibility criteria prior to discharge or at POD#8 because they are not able to take adequate nutrition by mouth, thus excluding the patient from randomization and further participation in the trial.

Another potential pitfall is that patients who randomize to have their tube feeding discontinued at discharge may (due to patient condition) require tube feedings to be resumed to supplement nutritional needs. Cross-over after randomization will be permitted for patient condition, although once randomized, patients will be analyzed by the original group.

[name], how do we construct randomization schema and power analysis to account for these limitations?

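### Section K replaces dropouts and losses to follow-up without separating losses before and after randomisation, and does not say whether replaced randomised patients stay in the analysis

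*Combined protocol and SAP*

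**What the plan says.** Section K sets an enrolment target, still a placeholder, in terms of evaluable patients. Its footnote defines evaluable by eligibility: the patient meets E.1 and is among those who "are not excluded from participation in the study by the exclusion criteria" in E.2. The footnote continues: "If there are patients who drop out of the study or are loss to follow-up, they will be replaced" until a minimum is reached, the minimum being a second blank number of "evaluable patients for specific aims 1 and 2".

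Section F states the rule for randomised patients: "once randomized, patients will be analyzed by the original group". Section L repeats it, and the full sentence shows its setting: "Cross-over after randomization will be permitted for patient condition, although once randomized, patients will be analyzed by the original group".

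On timing, Section F has the envelope opened before discharge, or at postoperative day 8 in patients eating adequately. The Section N table puts randomisation in the inpatient stay, after a re-check of eligibility. Section J compares quality of life, the primary outcome for Aim 1 under Section D, at 6 months with descriptive statistics. No section gives a missing-data method or says how non-completers are handled. The only patients expressly left out of the analysis (Section C) are those unable to take nutrition by mouth at day 8 or dependent on tube feeding at discharge.

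**The concern.** Replacing someone to reach a minimum of evaluable patients makes sense only if that person has stopped counting. A randomised patient who later drops out still satisfies the footnote's definition and would need no replacement. In use, then, the term drifts from eligible towards completed follow-up, and the text never says so.

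Two teams following Section K in good faith could analyse different populations: one all randomised patients, the other only those with 6-month data. The second choice matters if dropout depends on the assigned arm. That is plausible, though not documented. One arm is asked to keep feeding by tube for a month, and Section H.2 lists discomfort, diarrhoea and dumping among tube complications. The other arm relies on oral intake, which Section B expects may fall, sometimes enough to cause readmission. The final number would look complete in either case, so the loss would be hard to see in the report.

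**Working it through.** **Does the rule reach randomised patients?** Assignment is known by discharge at the latest (Section F). The 2-week visit and the 1-, 3- and 6-month assessments come after discharge (Section H.3, Section N table). A patient lost at any of these points has already been randomised, so the rule reaches randomised patients. It may also cover consented patients who leave before assignment, whom Section L expects; replacing those does no harm to the comparison.

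**Is there a figure to reproduce?** No. The sample size is blank, and no alpha, power, effect size, SD or dropout rate is given. Everything below is illustration on assumed values.

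**Patients left uncounted.** If a fraction d of randomised patients is lost and replaced, 100/(1 − d) must be randomised per 100 completers, rounded up:

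- d = 5%: 100/0.95 gives 106, so 6 uncounted
- d = 10%: 100/0.90 gives 112, so 12 uncounted
- d = 20%: 100/0.80 = 125, so 25 uncounted
- d = 30%: 100/0.70 gives 143, so 43 uncounted

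**Bias if only completers are analysed.** Let dropouts in an arm score g SD worse than completers. The arm's full mean equals the completer mean minus d × g, so the completer mean is too high by d × g. The between-arm difference is therefore biased by

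b = d_T × g_T − d_C × g_C,

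where T is the feeding arm and C is usual practice. For illustration take g equal in both arms, a true difference of zero, 100 completers per arm and a two-sided 5% test (the plan names no test). The chance of a false positive in the biased direction is P(Z > 1.96 − b√(n/2)). For b = 0.10: 0.10 × √50 = 0.707, 1.96 − 0.707 = 1.253, giving 10.5%.

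| d_C | d_T | g (SD) | b (SD) | False positive in that direction (nominal 2.5%) |
|---|---|---|---|---|
| 10% | 10% | 0.25 to 1 | 0 | 2.5% |
| 10% | 20% | 0.25 | 0.025 | 3.7% |
| 10% | 20% | 0.5 | 0.05 | 5.4% |
| 10% | 20% | 1 | 0.10 | 10.5% |
| 10% | 30% | 0.25 | 0.05 | 5.4% |
| 10% | 30% | 0.5 | 0.10 | 10.5% |
| 10% | 30% | 1 | 0.20 | 29.3% |

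Swapping the two dropout rates reverses the sign. Replacement does not enter the formula for b: it raises n, and at fixed b a larger n raises the false-positive rate.

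**The case against.** The best defence is that Section K is a recruitment footnote. Enrolling further patients does not delete earlier ones, and no passage says that replaced patients leave the analysis. This stands. A reader might infer that the replacement rule and the original-group rule cannot both be followed, but the documents do not support that: the trial could recruit replacements and still analyse everyone randomised. Moreover, the original-group statement is in both places the second half of a sentence on cross-over. It settles which arm a patient belongs to and does not address non-completers. The conflict with it is implied, not direct.

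Other stronger readings also fail:

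- **Relabelling through E.2.3.** The criterion ("Inability to provide informed consent or to complete testing or data collection") might be thought to let a non-completer be called excluded afterwards. It is an entry criterion, and the Section N footnote puts the eligibility re-check before randomisation.
- **Replacements as guaranteed completers.** They are newly enrolled patients and can drop out too.
- **Equal distortion of complications and readmissions.** Aim 2 complications have a 30-day window and are identified prospectively, and costs come from billing data. An unreturned 6-month form does not erase these.
- **A bias that must favour feeding.** That would need heavier loss in the feeding arm among patients doing badly. Section B gives reasons for poor outcomes without feeding as well, and a patient who stops the regimen may remain in follow-up as a cross-over.

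The defence also notes correctly that the bias is a missing-data bias, which deleting the replacement rule would not by itself remove. What it does not answer is Section K's contradiction with its own definition, or its silence on the analysis of replaced randomised patients.

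**Conclusion.** The point holds as a gap and an internal inconsistency, and should be fixed; it is not a proven breach of analysis by assigned group. Section K stops counting randomised patients who are lost, although they remain evaluable by its own definition, and leaves their place in the analysis open.

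The consequence is conditional. If the analysis is confined to completers and the product of dropout fraction and score deficit differs between arms, the 6-month quality-of-life comparison is biased by that difference. The range of 0.025 to 0.20 SD rests on assumed dropout of 10% against 20–30%, a deficit of 0.25 to 1 SD that is equal in both arms, and no true difference. If the products are equal, the bias is zero. The documents fix neither size nor direction.

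**What to change.** Change Section K, and Section J to match:

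1. Limit replacement to consented patients who fail the eligibility re-check or leave before the assignment is opened.
2. State that all randomised patients are analysed by original group, whether or not they complete follow-up, and use evaluable only in its eligibility sense.
3. For patients who stop the assigned regimen, continue the scheduled 1-, 3- and 6-month mail or telephone assessments and the collection of complications, readmissions and billing data, unless consent is withdrawn.
4. Allow for expected loss when the blank enrolment target is filled in, as N/(1 − d) with d stated and justified.
5. Analyse 6-month quality of life with a method that uses all available post-baseline assessments, for example a mixed model for repeated measures adjusted for baseline QLQ-C30, with a sensitivity analysis for missing data. Item 5 is needed because items 1 and 2 cannot supply scores that were never collected.

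The cost is protocol wording, a somewhat smaller number with complete data than open-ended replacement would give, and a little more analysis work. The follow-up contacts and billing data are already planned, so no new procedure is required.
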